6.3 PARTIAL DATE IMPUTATION

The following rules should be used when modifying partial or missing dates for reporting purposes such as defining on treatment flags.

A permanent new date variable should be created if there is a requirement to be used in determining flags, sort orders and other derived variables needed for a table, listing or figure. Imputed date variable names will be defined in the derived dataset specifications.

Original (raw) date variables must not be overwritten. Imputed dates will not be displayed in the listings.

General rules

Adverse events (AE) or prior and concomitant medications are considered to have started at the earliest possible date and end at the latest possible date.

In case of partial dates with missing day:

For any AE or concomitant medication starting during the month of first dose, the partial start date will be imputed at the date of first dose, taking the worst case scenario.

For any AE or concomitant medication starting after the month of first dose, the start date will be imputed at the first day of the month.

For any AE or concomitant medication starting before the month of first dose, the start date will be imputed at the last day of the month.

For any AE or concomitant medication, a partial end date will be imputed at the last day of the month or at the date of study discontinuation, whichever occurs first.

In case of partial dates with missing day and month:

For any AE or concomitant medication starting during the year of first dose, the partial start date will be imputed at the date of first dose, taking the worst case scenario.

For any AE or concomitant medication starting after the year of first dose, the partial start date will be imputed at the first of January.

For any AE or concomitant medication started before the year of first dose, the partial start date will be imputed as the last day of the year.

For any AE or concomitant medication, a partial end date will be imputed at the last day of the year or at the date of study discontinuation, whichever occurs first

Some examples are given below (YYYY-MM-DD).

In most cases, start dates are imputed as first day of the month or first day of the year.

Data Type	Start Date	Imputed Start Date	First dose	Date of disconti- nuation	End Date	Imputed End Date
Adverse Event, Prior/Concomit ant Meds	2017-02	2017-02-01	2016-12-17	_	2017-02	2017-02-29
Adverse Event, Prior/Concomit ant Meds	2017-02	2017-02-03	2017-02-03	-	2017-02	2017-02-29
Adverse Event, Prior/Concomit ant Meds	2017-02	2017-02-03	2017-02-03	-	2017-03	2017-03-31
Adverse Event, Prior/Concomit ant Meds	2017-03	2017-03-01	2017-02-03	-	2017-03	2017-03-31
Adverse Event, Prior/Concomit ant Meds	2017-01	2017-01-31	2017-03-03	_	2017-01	2017-01-31
Adverse Event, Prior/Concomit ant Meds	2016	2016-12-31	2017-02-03	2017-03-16	2017-03	2017-03-16
Adverse Event, Prior/Concomit ant Meds	2017	2017-02-03	2017-02-03	2017-04-08	2017-03	2017-03-31

Partial dates for initial diagnosis of PBC will be imputed as the 15th of the month if the month and the year are recorded, or the 1st of July if only the year is recorded.

Partial dates are not expected for efficacy-related assessments and death.

However, should a partial date be recorded for any efficacy-related assessment then this date will be imputed as the first day of the month if the month and the year are recorded or the latest between first of January and date of first dose if only the year is recorded.

In case of partial date for death, the date will be imputed as the day after the last visit/assessment date when the patient was known alive.

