# 9.2.3 Recording Adverse Events

As quality and precision of acquired AE data is of key importance, the Investigator should use the AE definitions provided in above sections and observe the following guidelines when completing the AE pages of the eCRF:

- Whenever possible, recognized medical terms should be used to describe AEs rather than colloquialisms (for example, 'influenza' rather than 'flu'), and abbreviations should be avoided.
- AEs should be described using a specific clinical diagnosis rather than component signs or symptoms, if this is available (for example, 'congestive heart failure' rather than 'dyspnea, rales and cyanosis'). However, signs and symptoms considered unrelated to an identified disease or syndrome should be reported as individual AEs in the eCRF.
- AEs occurring secondary to other events (e.g., sequelae or complications) should be identified by the primary cause. A primary AE, if clearly identifiable, generally represents the most accurate clinical term to record in the AE pages of the eCRF.

Additional guidance can be found in the eCRF completion conventions provided by the Sponsor.

For the purposes of this study, any detrimental change in the subject's condition, after signing the informed consent form (ICF) and up to completion of the 28-day follow-up period after the last administration of IMP, should be considered an AE. AEs should be followed-up in accordance with the procedures described in Section 9.2.4.

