8.10.1 Adverse Events (AEs)

All AEs will be coded using MedDRA dictionary. The version of the dictionary will be provided in the adverse events tables, figures and listing footnotes.

All information on AEs will be listed by subject.

Treatment-Emergent Adverse Events (TEAEs) will be defined as AEs that started on or after the date of the first dose of the received treatment.

AEs that occurred prior to the first dose of the received treatment and increased in severity and/or relationship after the first dose of the received treatment will also be regarded as TEAEs. If it is not possible to determine whether an AE is a TEAE due to a missing start date, the AE will be regarded as a TEAE unless the stop date indicates that the AE occurred prior to the first dose of the received treatment.

All reported TEAEs will be summarized.

The number and percentage of subjects experiencing the following categories of AEs will be summarized for each received treatment group and for all received treatment groups combined both overall and by system organ class and preferred term:

- TEAEs
- Related TEAEs
- Serious TEAEs
- Related and serious TEAEs
- TEAEs leading to study drug discontinuation
- TEAEs leading to study drug interruption
- Non-TEAEs

In addition, the number and percentage of subjects experiencing the following categories of AEs will be summarized for each received treatment group and for all received treatment groups combined by system organ class, preferred term and maximal severity:

- TEAEs
- Related TEAEs

For all system organ classes and preferred terms with a TEAE incidence rate of at least 5% over all received treatment groups combined, the number and percentage of subjects will be summarized for each received treatment group and for all received treatment groups combined by system organ class and preferred term.

Subjects will be counted only once within each system organ class, preferred term and severity.

- If a subject has experienced more than one adverse events coded within the same system organ class then this subject will be counted only once within that system organ class.
- If a subject has experienced more than one adverse events coded to the same preferred term within a system organ class then the subject will be counted only once for that preferred term and within that system organ class.

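### SAP 6.3 imputes partial start dates in the month or year of first dose to first dose without checking the end date, and the SAP does not say whether the 8.10.1 stop-date exception overrides this

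*SAP*

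**What the plan says.** SAP 6.3 states its scope as follows: "The following rules should be used when modifying partial or missing dates for reporting purposes such as defining on treatment flags". Two of its rules matter here.

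- Day missing: the trigger reads "For any AE or concomitant medication starting during the month of first dose". When it is met, the instruction is that "the partial start date will be imputed at the date of first dose, taking the worst case scenario".
- Day and month missing: the trigger reads "For any AE or concomitant medication starting during the year of first dose". The instruction does not differ.

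Neither rule mentions the end date. The general rule at the head of the section says that AEs and medications "are considered to have started at the earliest possible date and end at the latest possible date". Partial starts before the month (or year) of first dose go to the last day of that month (or year). Raw dates are kept, and imputed dates do not appear in listings.

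SAP 8.10.1 defines a TEAE as an AE that started on or after first dose. It then adds an exception, with the condition "If it is not possible to determine whether an AE is a TEAE due to a missing start date". Such an event counts as treatment-emergent "unless the stop date indicates that the AE occurred prior to the first dose of the received treatment".

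SAP 8.5 classes a medication as prior if it ended before first dose. It classes a medication as concomitant if it started on or after first dose, or started earlier and was still in use at first dose.

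Protocol 9.2.3 collects AEs "after signing the informed consent form (ICF) and up to completion of the 28-day follow-up period". SAP Table 1 places screening at Day -28 to -7. AEs that begin and end before dosing will therefore be in the database.

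**The concern.** Setting an uncertain start to first dose is a reasonable conservative choice when the event might have begun on treatment. It is not conservative when the recorded end date already shows that the event was over before any capsule was taken. The rule then replaces known information with a date the data contradict.

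What is at stake is the TEAE flag. If the imputed start is taken at face value, the event moves from the planned non-TEAE summary into the TEAE and maximum-severity tables. Because imputed dates are not listed, a reader of the listings would not see the start-after-end conflict that caused it. For medications, the prior and concomitant categories stop being mutually exclusive.

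**Working it through.** **1. The plan's own examples.** SAP 6.3 gives seven worked rows. Applying its rules literally reproduces all seven imputed start dates and five of the seven imputed end dates. The other two rows show 29 February 2017, which does not exist; the rule gives 28 February. Three rows set the start to first dose, and in all three the end falls after first dose. No example covers an end before first dose under this rule.

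**2. Constructed cases, first dose 20 March 2018.**

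| Recorded start | Recorded end | Imputed start (6.3) | End used | End minus start | TEAE on imputed start | TEAE if 8.10.1 exception covers partial dates |
|---|---|---|---|---|---|---|
| 2018-03 | 12 Mar 2018 | 20 Mar 2018 | 12 Mar 2018 | -8 days | yes | no |
| 2018 | 28 Feb 2018 | 20 Mar 2018 | 28 Feb 2018 | -20 days | yes | no |
| 2018 | 2018-02 | 20 Mar 2018 | 28 Feb 2018 | -20 days | yes | no |
| 2018-03 | 2018-03 | 20 Mar 2018 | 31 Mar 2018 | +11 days | yes | yes |
| 2018-02 | 10 Feb 2018 | 28 Feb 2018 | 10 Feb 2018 | -18 days | no | no |

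Rows 1 to 3 are the defect. Row 4 shows its limit: if the end is also known only to the first-dose month, it goes to month end and no contradiction arises. Row 5 shows that the last-day-of-month rule can also put a start after its end, although TEAE status does not change.

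**3. The two sections side by side.** SAP 6.3 names partial and missing dates as separate things; 8.10.1 names only missing ones. SAP 6.3 also has no rule for a wholly missing start date, so 8.10.1 can be read as filling just that gap. Against this, the raw dates are retained, and on the raw data a start known only to the month does leave TEAE status open, so the exception can also be read to apply. Nothing in the SAP settles which governs. The same AE is a TEAE on one reading and not on the other.

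**4. Medications.** Take row 1 as a medication. Its end, 12 March, is before first dose, so it is prior. Its imputed start, 20 March, is the first-dose date, so it is also concomitant. SAP 8.5 has no stop-date exception for this case.

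**5. Size per case.** The planned arm size is 34 (SAP 5.4), so one subject is 1/34 = 2.9 percentage points. A given incidence moves only if that subject has no other TEAE in the same category.

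**The case against.** The strongest reply is that the SAP already has the right check. SAP 8.10.1 says that a stop date before first dose keeps an AE out of the TEAE set, and a sensible programmer would apply it to partial dates. This stands in part. A reader might infer from 6.3 that such AEs will certainly be counted as TEAEs; the documents do not support that, because the exception can be read to include partial starts. What remains is that the SAP does not say so and gives no precedence.

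Other stronger readings also go too far.

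- **Negative durations in the results.** They arise in the derived dates, but no AE duration output is planned and imputed dates are not listed.
- **Related TEAEs.** Under Protocol 9.2.1.2, the possible and probable categories both require a temporal link to administration, so an event over before dosing should receive neither. Only a missing relationship defaults to related.
- **A high frequency.** For a first dose on a random day of a 30-day month, 434/30 = 14.5 of 28 preceding days, or 52%, fall in the same month. That is a share of screening days and not an error rate. The error also needs an AE that ended before dosing, an incomplete start, and an end precise enough to be placed before first dose. AEs are recorded at both Visits 1 and 2, and incomplete entries are queried.

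On medications, the first-dose rules in 6.3 mention only concomitant ones, so one already prior by its end date might be held to fall outside them. But the section's general rule and its example rows name prior and concomitant medications together, and 6.3 has no separate rule for prior ones.

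**Conclusion.** The point holds as a minor rule defect. SAP 6.3 can place an imputed start after a known pre-dose end. Whether that AE is then flagged as a TEAE depends on an unstated choice between 6.3 and 8.10.1. For medications, the overlap between prior and concomitant follows from 8.5 however 8.10.1 is read, provided the 6.3 rule is applied to them.

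Few cases are expected, and the documents give no basis for a count. Events over before dosing cannot be caused by the assigned treatment, so no direction between arms is expected. Each case would move one subject, up to 2.9 percentage points of an arm's TEAE incidence, taking 34 subjects per arm. Efficacy is unaffected.

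**What to change.** - **SAP 6.3:** apply the first-dose rule only if the end date is missing, ongoing, or on or after first dose. Under every start-date rule, including those for starts before the month or year of first dose, never impute a start later than the end date (as recorded, or as imputed if the end is itself partial). Add a worked row with an end before first dose, and correct the two 29 February 2017 entries.
- **SAP 8.10.1:** extend the exception from missing start dates to missing or partial ones, and state that it takes precedence over a date imputed under 6.3.
- **SAP 8.5:** class any medication with an end date before first dose as prior only. The cross-reference there to section 6.2 for partial dates should point to 6.3.

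The cost is a few sentences in the SAP and one condition in the derivation program. It needs no new data and should be settled before unblinding.

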### **10.4.3.2 Primary Efficacy Analysis**

The mean of all assessments, including repeat assessments, prior to first dose will be considered as the baseline value for the analysis.

Due to the small sample size the primary analysis will be conducted using a stepwise approach. The percent change from baseline to Week 24 in serum GGT will be analyzed using an Analysis of Covariance (ANCOVA) with treatment and disease severity as fixed effects, and baseline GGT as a continuous covariate. If the normality assumption for the analysis is not met then the percent change from baseline in GGT at Week 24 will be analyzed non-parametrically through a stratified Wilcoxon Mann-Whitney (van Elteren) test. The normality assumption will be assessed through the examination of diagnostic residual plots. Further details and assumption checking will be provided in the SAP.

The difference between each dose of GKT137831 and placebo will be calculated, along with 95% and 97.5% confidence intervals of the difference (to account for Hochberg adjustment).

The primary analysis will be performed using the ITT population and a sensitivity analysis will be done using the PP population. If the Wilcoxon Mann-Whitney test is used, a subgroup analysis for disease severity will also be performed.

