6.4 VISIT WINDOWING

Visit windowing will be considered only for efficacy and pharmacodynamic assessments.

The halfway point corresponding to the visits will be considered in relation to the date of first dose. Efficacy assessments are planned to be conducted at Week 2, Week 6, Week 12, Week 18, Week 24 and Week 28 visits. The following windowing rules will be taken into account to establish the visit corresponding to each efficacy and pharmacodynamic assessment:

- Week 2: any efficacy or pharmacodynamic assessment performed between 2 to 28 days after the first dose;
- Week 6: any efficacy or pharmacodynamic assessment performed between 29 days to 63 days after the first dose;
- Week 12: any efficacy or pharmacodynamic assessment performed between 64 days to 105 days after the first dose;
- Week 18: any efficacy or pharmacodynamic assessment performed between 106 days to 147 days after the first dose;
- Week 24: any efficacy or pharmacodynamic assessment performed between 148 days to 182 days after the first dose;
- Week 28: any efficacy or pharmacodynamic assessment performed between 183 days to 203 days after the first dose;

If two (or more) assessments are recorded within a visit window, the closer (closest) to the halfway point will be taken into account for the analyses. If two assessments within a visit window are the same number of days from the halfway point, the second one will be taken into account for the summaries assuming that it is more reliable than the first one.

No programmatic windowing of visits will be considered for safety data. Post-baseline data will be presented according to the visit at which it was collected on the eCRF or as described in this SAP.

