6.5 BASELINE

Baseline is defined as the last non-missing value/result where assessment date is less than or equal to the date of first dose, unless otherwise specified for individual assessments.

Baseline will be determined based on all assessments, including additional assessments.

Change from baseline is defined as the difference between the post-baseline assessment value and the baseline value.

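### For an efficacy assessment with a partial date, SAP 6.3 to 6.5 can move the value out of its own visit window or make it a baseline candidate, although the eCRF visit is known (minor)

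*SAP*

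**What the plan says.** SAP 6.3 first notes that "Partial dates are not expected for efficacy-related assessments and death". It then gives a rule in case one occurs. For a missing day, "this date will be imputed as the first day of the month if the month and the year are recorded". For a missing day and month, the date is set by a second clause: "or the latest between first of January and date of first dose if only the year is recorded".

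SAP 6.4 assigns efficacy and pharmacodynamic results to visits by days since first dose, for example "Week 24: any efficacy or pharmacodynamic assessment performed between 148 days to 182 days after the first dose". The earliest post-baseline window takes "any efficacy or pharmacodynamic assessment performed between 2 to 28 days after the first dose". When two results share a window, the one nearest the halfway point is used. The eCRF visit is used for safety data only.

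SAP 6.5 states: "Baseline is defined as the last non-missing value/result where assessment date is less than or equal to the date of first dose". It adds: "Baseline will be determined based on all assessments, including additional assessments". It gives no rule for two values dated on the day of first dose, and nothing in 6.3 to 6.5 bars a result recorded at a post-baseline visit from counting as baseline. Protocol 10.4.3.2 defines the primary-analysis baseline differently: "The mean of all assessments, including repeat assessments, prior to first dose will be considered as the baseline value for the analysis".

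**The concern.** The rule replaces something known, the eCRF visit, with something invented, a date, and then lets the invented date decide the visit. Both clauses give a date no later than the true one for any post-baseline result, so such a value is never moved later and is often moved earlier. A value moved far enough leaves its own window. If it lands on the day of first dose, an on-treatment result satisfies the baseline definition.

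At stake is a subject's value at a scheduled visit or, in the extreme case, the reference from which all that subject's changes are computed. The records most open to a partial date are those that sites enter by hand: the paper PBC-40 and pruritus VAS (protocol 14.1) and, presumably, elastography. Clinical laboratory results come from a central laboratory.

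**Working it through.** **Inputs.** Scheduled days are 14, 42, 84, 126, 168 and 196 after first dose (Weeks 2, 6, 12, 18, 24 and 28), with visits within 3 days of schedule (protocol 7.3 and 7.4). The windows are from SAP 6.4, the imputation from 6.3 and the baseline condition from 6.5. *Assumption:* first-dose dates are uniform over a 365-day year. The protocol plans enrolment over 7-8 months, so the real mix may differ.

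**The plan's own windows.** The upper limits are midpoints of the scheduled days: (14+42)/2 = 28, (42+84)/2 = 63, (84+126)/2 = 105, (126+168)/2 = 147, (168+196)/2 = 182. The last is 196+7 = 203. All six agree with SAP 6.4.

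**Month-only date.** A result on day *d* of the month moves back *d* − 1 days.
- Week 24 can lose 168 − 148 = 20 days and stay in its window. Week 12 can lose 84 − 64 = 20.
- Each therefore leaves its window when *d* ≥ 22. Days in a year with *d* ≥ 22: 365 − 12×21 = 113, and 113/365 = **31.0%**.
- With a visit *j* days off schedule the count is 365 − 12×(21+*j*). Averaged over *j* = −3 to +3 it is again 113.
- The largest move is 30 days. Week 24 falls no earlier than 168 − 3 − 30 = 135 (Week 18 window, 106-147), and Week 12 no earlier than 84 − 3 − 30 = 51 (Week 6 window, 29-63). A record that moves always lands in the previous window.

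**Year-only date.** If the visit falls in the year of first dose, the imputed date is the first-dose date.

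| Visit | Tie with Day 1 | Right window | Earlier window or none |
|---|---|---|---|
| Week 24 | 365 − 168 = 197; 197/365 = **54.0%** | 1 January 148-168 days after first dose: 21/365 = 5.8% | 365 − 197 − 21 = 147; 40.3% |
| Week 12 | 365 − 84 = 281; 281/365 = **77.0%** | 1 January 64-84 days after first dose: 21/365 = 5.8% | 365 − 281 − 21 = 63; 17.3% |

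The tie depends wholly on when the subject started. For Week 24 it is certain for first doses from 1 January to 16 July and impossible after that.

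**Examples.**
- First dose 10 May 2018, Week 24 visit 25 October. Dated October 2018, it becomes 1 October, day 144, and is read as Week 18. Dated 2018, it becomes 10 May and is a baseline candidate.
- First dose 5 March 2018, Week 12 visit 28 May. Dated May 2018, it becomes 1 May, day 57, and is read as Week 6.

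**From wrong window to analysed value.**
- *A true Week 18 result is not displaced by a month-only Week 24 record.* The moved value lies at day 135 or later, at least 8.5 days from the window midpoint (106+147)/2 = 126.5. A true Week 18 visit on days 123-129 is at most 3.5 days from it.
- *Elastography* is scheduled only at baseline and Week 24 (protocol 8.1.5). SAP 6.2 excludes liver stiffness from LOCF, and SAP 8.7.2 requires values at both visits. A Week 24 scan read as Week 18 drops the subject.
- *PBC-40 and VAS at Week 12.* Read as Week 6, where neither is scheduled, the result is lost from Week 12. It also cannot be carried forward, because LOCF accepts only values from Week 12 onward.
- *PBC-40 and VAS at Week 24.* Read as Week 18, the result is normally the last value from Week 12 onward, so LOCF returns the same number to Week 24. After a year-only tie it does not: LOCF would use the Week 12 value.

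**The case against.** The strongest reply is that this almost never happens. The SAP expects no partial efficacy dates, the capture system checks for incomplete data (protocol 14.1), and errors are queried with sites (protocol 14.3). GGT comes from the central laboratory. The rule was fixed in advance and takes no account of arm, and PBC-40 and VAS are only summarised. All of this stands. It limits how many records are affected and makes between-arm bias hard to argue, but the rule was written for exactly these records.

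A reader might infer that about a third to nearly all partial-date records would give a wrong analysed value. The documents do not support that. The percentages count records in the wrong window or eligible as baseline. The halfway-point rule and LOCF prevent many of those from changing a number.

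A reader might also expect off-drug Week 28 results to be analysed as Week 24. A month-only date does put 54% of Week 28 records in the Week 24 window, but with a true Week 24 result present the misplaced value is chosen in about 10% of records at most. Neither questionnaires nor elastography are scheduled at Week 28, so this concerns blood results.

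Nor does every imputed date move earlier. A year-only screening record moves later, to first dose, if first dose is in the same year, and a month-only result from the 1st does not move. A month-only Week 2 result dated before first dose does not replace Day 1 under SAP 6.5, which takes the last value, though it could enter the protocol's mean of pre-dose values.

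**Conclusion.** The point holds as a minor defect. Taken together, SAP 6.3, 6.4 and 6.5 give a rule that often misplaces a post-baseline efficacy value with a partial date. Under uniform first-dose dates, 31% of month-only Week 24 and Week 12 records fall in the previous window. Among year-only records, 54% at Week 24 and 77% at Week 12 tie with Day 1 for baseline, and the tie is unresolved.

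The likely damage is a few values missing at their own visit, chiefly Week 24 elastography and Week 12 PBC-40 or VAS. The documents give no frequency of partial dates, so the number of affected records cannot be estimated. They do not support reading this as a threat to the primary GGT analysis.

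**What to change.** Replace the efficacy sentence in SAP 6.3 with:

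> An efficacy assessment with an incomplete date is assigned to the visit under which it was recorded in the eCRF, and no date is imputed for windowing. A value recorded at a post-baseline visit is never used as baseline. An unscheduled assessment with an incomplete date is listed but not windowed.

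This treats these few records as SAP 6.4 already treats safety data, and is closer to protocol 10.4.3.8, which summarises by-visit data whatever the window. It costs one paragraph and one programming condition. The downside is that a partial-date record from a visit held far off schedule keeps its nominal visit.
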